12. Clinically significant abnormal ECG including but not limited to, a corrected QT interval calculated using Fridericia's correction ($QTcF = QT/RR^{0.33}$) $> 450 \text{ msec}$, or ventricular and/or atrial premature contractions that are more frequent than occasional, and/or as couplets or higher in grouping.

13. Known hypersensitivity to berotralstat or any of its formulation excipients.

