7.3.2. Subject Discontinuation from Study Drug

A subject will be permanently discontinued from study drug for any of the following reasons, which will be recorded in the source documents and CRF:

- Emergence of any laboratory abnormality or AE that in the judgment of the investigator compromises the ability of the subject to continue study-specific procedures or it is considered not to be in the subject's best interest to continue in the study due to an altered benefit-risk profile.
- Subsequent determination that inclusion/exclusion criteria were not met.
- Intercurrent illness or emergence of a new illness/medical condition that would, in the judgment of the investigator, affect assessments of clinical status to a significant degree.
- Subject noncompliance with study drug or to the protocol.
- The subject has a confirmed QTcF > 500 msec (if there is an associated C_{max} exceeding the adult range, the dose may first be interrupted and/or reduced; see Sections 11.2.1 and 11.2.2).
- The subject has a confirmed QTcF increase of more than 60 msec from the mean QTcF value calculated from triplicate ECGs recorded at the Baseline visit and a simultaneous absolute QTcF > 460 msec (if there is an associated C_{max} exceeding the adult range, the dose may first be interrupted and/or reduced; see Sections 11.2.1 and 11.2.2).

- Pregnancy in a female subject.

Discontinuation of study drug should be considered for a subject if any of the following thresholds are met and confirmed by repeat measure

- ALT or AST $> 8\times$ upper limit of normal (ULN)
- ALT or AST $> 5\times$ ULN for more than 2 weeks
- ALT or AST $> 3\times$ ULN and (total bilirubin $> 2\times$ ULN or international normalized ratio [INR] > 1.5)
- ALT or AST $> 3\times$ ULN with the appearance of fatigue, nausea, vomiting, right upper quadrant pain or tenderness, fever, rash and/or eosinophilia ($> 5\%$)

Subjects are not eligible to receive berotralstat in Parts 2 or 3 if they discontinue prior to completing Parts 1 or 2, respectively.

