10.4. Weight/Height/Body Mass Index

Subject weight is important for this study as the dose of berotralstat will be based on subject weight. Therefore, the site should be diligent in accurately taking and recording subject weight. Subjects should be weighed in light clothing with shoes and other heavier items (eg, belts or phones) removed. Heavier outer clothing (eg, jackets or sweaters) should also be removed.

Height should be recorded at the indicated visits. Body mass index (BMI) should be calculated at all visits where weight and height are measured using the following formula:

$$\text{BMI} = \text{weight (kg)} / \text{height (m)}^2$$

10.5. 12-lead Electrocardiograms

A standard bedside or routine 12-lead ECG machine that calculates heart rate and measures the PR, QRS, QT, RR, and QTc intervals will be used. Prior to obtaining an ECG, subjects should rest quietly for at least 10 minutes. Resting may be in a supine position or other position (eg, on the P/C's lap) as age appropriate for the subject.

Qualified site personnel should review the ECGs and automated findings in real time for gross abnormalities and interval measurements of concern (absolute readings and for post-baseline ECGs, a change from baseline). For all ECGs, the clinical interpretation of the ECG and calculated QTc should be recorded directly on a hard copy of the ECGs. Copies of the ECGs may be requested by the sponsor. All subject identifiers will be masked prior to provision to the sponsor.

Baseline (pre-dose) ECGs will be obtained in triplicate (ie, 3 separate readings taken at 1- to 5-minute intervals) with baseline values calculated from an average of the 3 readings. All other ECGs will be single assessments.

An ECG should be repeated for a change from baseline in QTc > 60 msec or a QTc interval > 500 msec.

If AEs commonly associated with prolonged QTc interval (eg, unexplained intermittent or continuous lightheadedness, syncope, palpitation, chest pain) are reported or the dose is modified, additional ECGs should be recorded. ECGs obtained due to dose modification should be taken approximately 2 to 6 weeks after dose modification and should be aligned with PK blood sample timelines described in Section 10.9.1 to the extent possible.

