11.1.1.4. Definition of Severity

All AEs and SAEs will be assessed (graded) for severity by the investigator and classified using the Division of AIDS (DAIDS) table for grading the severity of adult and pediatric AEs (Publish date July 2017). Any AEs not covered by the DAIDS table will be assessed and classified into 1 of 5 clearly defined categories as follows:

- Mild:** (Grade 1): Mild symptoms causing no or minimal interference with usual social & functional activities with intervention not indicated.
- Moderate:** (Grade 2): Moderate symptoms causing greater than minimal interference with usual social & functional activities with intervention indicated.

Severe: (Grade 3): Severe symptoms causing inability to perform usual social & functional activities with intervention or hospitalization indicated.

Life-threatening: (Grade 4): Potentially life-threatening symptoms causing inability to perform basic self-care functions with intervention indicated to prevent permanent impairment, persistent disability, or death.

Death: (Grade 5): Indicates death related to the AE.

The investigator should report the highest severity experienced during the course of the event. It is important to distinguish between serious and severe AEs. Severity is a measure of intensity, defined above, whereas seriousness is defined by the criteria under Section 11.1.1.4. An AE of severe intensity may or may not be considered serious. An example would be a severe headache that does not result in any serious outcome is a non-serious AE; conversely, a mild event that results in hospitalization is a serious AE.

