Hemorrhage (with significant acute blood loss)	NA	Symptoms AND No transfusion indicated	Symptoms AND Transfusion of ≤ 2 units packed RBCs indicated	Life-threatening hypotension OR Transfusion of > 2 units packed RBCs (for children, packed RBCs > 10 cc/kg) indicated
Prolonged PR Interval or AV Block Report only one > 16 years of age	PR interval 0.21 to < 0.25 seconds	PR interval ≥ 0.25 seconds OR Type I 2 nd degree AV block	Type II 2 nd degree AV block OR Ventricular pause ≥ 3.0 seconds	Complete AV block
≤ 16 years of age	1 st degree AV block (PR interval $>$ normal for age and rate)	Type I 2 nd degree AV block	Type II 2 nd degree AV block OR Ventricular pause ≥ 3.0 seconds	Complete AV block
Prolonged QTc Interval²	0.45 to 0.47 seconds	> 0.47 to 0.50 seconds	> 0.50 seconds OR ≥ 0.06 seconds above baseline	Life-threatening consequences (e.g., Torsade de pointes, other associated serious ventricular dysrhythmia)
Thrombosis or Embolism Report only one	NA	Symptoms AND No intervention indicated	Symptoms AND Intervention indicated	Life-threatening embolic event (e.g., pulmonary embolism, thrombus)

² As per Bazett's formula.

Dermatologic

PARAMETER	GRADE 1 MILD	GRADE 2 MODERATE	GRADE 3 SEVERE	GRADE 4 POTENTIALLY LIFE- THREATENING
Alopecia (scalp only)	Detectable by study participant, caregiver, or physician AND Causing no or minimal interference with usual social & functional activities	Obvious on visual inspection AND Causing greater than minimal interference with usual social & functional activities	NA	NA
Bruising	Localized to one area	Localized to more than one area	Generalized	NA
Cellulitis	NA	Non-parenteral treatment indicated (e.g., oral antibiotics, antifungals, antivirals)	IV treatment indicated (e.g., IV antibiotics, antifungals, antivirals)	Life-threatening consequences (e.g., sepsis, tissue necrosis)
Hyperpigmentation	Slight or localized causing no or minimal interference with usual social & functional activities	Marked or generalized causing greater than minimal interference with usual social & functional activities	NA	NA
Hypopigmentation	Slight or localized causing no or minimal interference with usual social & functional activities	Marked or generalized causing greater than minimal interference with usual social & functional activities	NA	NA
Petechiae	Localized to one area	Localized to more than one area	Generalized	NA

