- 7. History of severe hypersensitivity to multiple medicinal products or severe hypersensitivity/anaphylaxis with unclear etiology.
- 8. Current participation in any other investigational drug study or received another investigational drug within 30 days of enrollment; not willing to refrain from participation in another clinical study after

enrollment and for the duration of the study. [Note: drugs/vaccines approved under Food and Drug Administration (FDA) emergency use authorization (or country-specific analogous regulations) are not considered excluded or prohibited under this criterion.]

9. An immediate family relationship to either sponsor employees, the investigator, or employees of the study site named on the delegation log.
10. Any result at screening that, in the opinion of the investigator, is clinically significant and relevant for this study.
11. Any clinically significant medical condition or medical history (including altered mental status) that, in the opinion of the investigator or sponsor, would interfere with the subject's safety or ability to participate in the study. Examples include but are not limited to active malignancy under treatment, uncontrolled cardiovascular disease, organ dysfunction requiring supportive care.
12. Clinically significant abnormal ECG including but not limited to, a corrected QT interval calculated using Fridericia's correction ($QTcF = QT/RR^{0.33}$) > 450 msec, or ventricular and/or atrial premature contractions that are more frequent than occasional, and/or as couplets or higher in grouping.
13. Known hypersensitivity to berotralstat or any of its formulation excipients.

Investigational product, dosage, and mode of administration:

Berotralstat 150 mg capsules in multidose bottles and granules for oral administration packaged in unit-dose packets will be taken orally, once daily (QD), with food. The doses for Cohorts 1, 2, 3, and 4 are shown in the table below. Based on safety assessments and/or the PK data analyses, the weight bands for Cohorts 3 and 4 may be adjusted if needed.

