8.6. Values of Clinical Concern

QTcF intervals >500 msec or a change from baseline in QTcF > 60 msec and a simultaneous absolute QTcF > 460 msec are of clinical concern.

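### QT adverse events are graded on a DAIDS row defined by Bazett, while entry, stopping and SAP ECG rules use Fridericia, so one on-treatment ECG can be reported as grade 2 or 3 and as QTcF 450 msec or below

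*Protocol*

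**What the plan says.** **Rules on Fridericia.** Protocol 7.2.2, criterion 12, excludes a "Clinically significant abnormal ECG including but not limited to, a corrected QT interval calculated using Fridericia's correction" above 450 msec, with QTcF = QT/RR^0.33. Protocol 7.3.2 has two QT stopping rules. One begins "The subject has a confirmed QTcF > 500 msec". The other begins "The subject has a confirmed QTcF increase of more than 60 msec from the mean QTcF value" and also requires an absolute QTcF above 460 msec. SAP 8.6 says that the same two conditions "are of clinical concern". SAP 11.5 tabulates QTcF in bands cut at 450, 470 and 500 msec, and increases from baseline in bands cut at 30 and 60 msec.

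**Rule on Bazett.** Under Protocol 11.1.1.4, adverse events are "classified using the Division of AIDS (DAIDS) table for grading the severity of adult and pediatric AEs", and SAP 11.1 repeats this. In Protocol Appendix 15.1 the Prolonged QTc Interval row sets grade 1 at 0.45 to 0.47 s, grade 2 above 0.47 to 0.50 s, and grade 3 above 0.50 s or at least 0.06 s above baseline. Footnote 2 to that row reads "As per Bazett's formula".

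**Rule with no formula named.** Protocol 10.5, repeated in Table 2 footnote p, states: "An ECG should be repeated for a change from baseline in QTc > 60 msec or a QTc interval > 500 msec".

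**The concern.** The SAP's QTcF bands and the DAIDS grades share the cut-offs 450, 470 and 500 msec but apply them to different quantities. Read literally, one report can place the same ECG in the lowest QTcF band and in a grade 2 or 3 adverse event row. Because Bazett over-corrects relative to Fridericia as heart rate rises, a change in heart rate alone can move the grade.

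The severity of adverse events is a secondary endpoint (Protocol 5.2.2), and grade 3 or 4 events have their own planned tables (SAP Table 7, outputs 14.3.1.7 and 14.3.1.8). Minimum cohort sizes are 3 or 4, so one child whose grade depends on the formula is 1/4 = 25% to 1/3 = 33% of a minimum-size cohort. Protocol 4.4.5 notes a labelled warning on QT prolongation, which concerns doses above 150 mg daily.

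**Working it through.** The documents give no computed figure on this point, so there is none to reproduce.

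**Inputs.** QTcF = QT/RR^0.33 (Protocol 7.2.2). Bazett is QTcB = QT/RR^0.5. RR = 60/heart rate, in seconds. The DAIDS cut-offs are those of Appendix 15.1. Heart rates are my assumption, with 70 to 140 bpm taken as the range.

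**Conversion.** For one ECG, QTcB = QTcF × RR^(0.33 − 0.5) = QTcF × (heart rate/60)^0.17. The factor is 1 at 60 bpm and exceeds 1 above it.

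| Heart rate (assumed) | Factor | QTcB if QTcF = 420 | QTcB if QTcF = 450 |
|---|---|---|---|
| 80 | 1.050 | 441.1 (ungraded) | 472.6 (grade 2) |
| 100 | 1.091 | 458.1 (grade 1) | 490.8 (grade 2) |
| 120 | 1.125 | 472.5 (grade 2) | 506.3 (grade 3) |

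With exponent 1/3 in place of 0.33, the QTcF 450 column becomes 472.1, 490.0 and 505.1, with the same grades.

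**Where the grades begin.** Solving for heart rate gives 60 × (QTcB/QTcF)^(1/0.17). At QTcF 450, QTcB passes 470 at 77.5 bpm and 500 at 111.5 bpm (77.9 and 112.9 with exponent 1/3). For a QTcF of 450 or below to reach grade 3 on absolute value, QTcF must exceed about 444 msec at 120 bpm, or 433 msec at 140 bpm. At QTcF 400 the grade is at most 1 up to 140 bpm (400 × 1.155 = 462).

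**Two on-treatment illustrations,** each assuming that the investigator has judged the finding to be an adverse event:

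- QTcF stays at 420 while heart rate goes from 80 to 120 bpm. QTcB goes from 441.1 to 472.5, a rise of 31.4 msec, so the grade goes from none to 2 with no change in QTcF.
- QTcF goes from 420 to 450 over the same heart-rate change. QTcB goes from 441.1 to 506.3, a rise of 65.2 msec, which meets both limbs of grade 3. SAP 11.5 places the ECG at 450 or below with an increase of 30 to 60 msec. Neither SAP 8.6 condition nor either stopping rule is met.

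**Does anything override the footnote?** The fallback scale in Protocol 11.1.1.4 covers only events absent from the DAIDS table, and prolonged QTc is in it. The DAIDS instructions apply a row to children and adults alike where no age split is given. The QTc row has none. The plan's stated modifications of DAIDS (Protocol 12.2.5, SAP 6.7.6) concern laboratory values. None addresses QTc.

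**The case against.** The strongest reply is that ECG values are not graded automatically. Under Protocol 11.1.1.1 a protocol-mandated finding is an adverse event only if it has worsened from baseline and is clinically significant. This stands, and it rules out a tempting stronger reading: that a child who passes the 450 msec entry limit is already grade 2 or 3 before any drug. The arithmetic can put such a child's QTcB in those ranges, but no grade is assigned to a pre-drug ECG by itself. Entry is also not decided by the number alone. Criterion 12 is open-ended, and criterion 10 covers any clinically significant screening result.

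Second, the main QT evaluation does not use the grade. The QTcF bands in SAP 11.5 and the Torsade/QT query table in SAP 11.1 are the same whichever formula governs grading. This also stands and limits the reach of the point.

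Third, the sizes rest on assumed heart rates, and grade 3 with QTcF at or below 450 needs a fast rate and a QTcF close to 450, unless the rise limb is met. A reader might go further and infer that the distortion is tied to weight cohort and dose, because smaller children tend to have faster hearts. The documents give no heart rates by age or cohort and plan no inferential comparison, so they do not support that claim.

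Fourth, the creatinine modification might be read as a precedent that should have been extended to QTc. It is a weak one, since the plan grades all laboratory results against DAIDS and plans no such grading of ECGs.

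None of this says which formula a site should use once a QT event is reported. The DAIDS instruction to take the higher grade when two are possible would, if anything, push an unsure site towards Bazett.

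**Conclusion.** The inconsistency is real and confined to the severity grade of reported QT adverse events. If the plan is followed as written, such an event can be graded 2 or 3, or shift grade with heart rate, while the SAP's QTcF table shows the same ECG at 450 msec or below. Bazett exceeds Fridericia by about 5%, 9% and 12 to 13% at 80, 100 and 120 bpm. How many children this would touch cannot be estimated, because the documents give neither heart rates nor a QTcF distribution. It should be corrected, but it does not threaten the primary endpoint or the planned QTcF summaries.

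The unqualified QTc in the repeat-ECG rule is a separate ambiguity. A reader might infer that it must mean QTcF because the stopping rules need a confirmed QTcF. The text does not say so.

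**What to change.** In Protocol 11.1.1.4 and SAP 11.1, state that for adverse event grading the DAIDS QTc cut-offs are applied to QTcF, with change measured from the mean of the triplicate baseline QTcF. SAP 6.7.6 and the grading text in Protocol 12.2.5 concern laboratory values and are not the place for it. QTcF is already derived and reported, so the cost is wording, plus reduced comparability with studies graded on Bazett.

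One difference will remain. DAIDS grade 3 is met by a rise of at least 60 msec alone, whereas SAP 8.6 needs a rise above 60 msec together with QTcF above 460. For example, QTcF going from 395 to 458 is a rise of 63 msec: grade 3, but outside SAP 8.6. A table footnote should say so.

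Separately, the sponsor should reconcile Protocol 10.5 and Table 2 footnote p with the confirmed-QTcF rules in Protocol 7.3.2. No trigger is proposed here.

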Appendix A.

Total Bilirubin Table for Term and Preterm Neonates

PARAMETER	GRADE 1 MILD	GRADE 2 MODERATE	GRADE 3 SEVERE	GRADE 4 POTENTIALLY LIFE- THREATENING
Total Bilirubin¹⁸, High (mg/dL; $\mu\text{mol/L}$) ¹⁹				
Term Neonate²⁰ < 24 hours of age	4 to < 7 68.4 to < 119.7	7 to < 10 119.7 to < 171	10 to < 17 171 to < 290.7	≥ 17 ≥ 290.7
24 to < 48 hours of age	5 to < 8 85.5 to < 136.8	8 to < 12 136.8 to < 205.2	12 to < 19 205.2 to < 324.9	≥ 19 ≥ 324.9
48 to < 72 hours of age	8.5 to < 13 145.35 to < 222.3	13 to < 15 222.3 to < 256.5	15 to < 22 256.5 to < 376.2	≥ 22 ≥ 376.2
72 hours to < 7 days of age	11 to < 16 188.1 to < 273.6	16 to < 18 273.6 to < 307.8	18 to < 24 307.8 to < 410.4	≥ 24 ≥ 410.4
7 to 28 days of age (breast feeding)	5 to < 10 85.5 to < 171	10 to < 20 171 to < 342	20 to < 25 342 to < 427.5	≥ 25 ≥ 427.5
7 to 28 days of age (not breast feeding)	1.1 to < 1.6 x ULN	1.6 to < 2.6 x ULN	2.6 to < 5.0 x ULN	≥ 5.0 x ULN
Preterm Neonate²⁰ 35 to < 37 weeks gestational age	Same as for Total Bilirubin, High, Term Neonate (based on days of age).	Same as for Total Bilirubin, High, Term Neonate (based on days of age).	Same as for Total Bilirubin, High, Term Neonate (based on days of age).	Same as for Total Bilirubin, High, Term Neonate (based on days of age).
32 to < 35 weeks gestational age and < 7 days of age	NA	NA	10 to < 14 171 to < 239.4	≥ 14 ≥ 239.4
28 to < 32 weeks gestational age and < 7 days of age	NA	NA	6 to < 10 102.6 to < 171	≥ 10 ≥ 171
< 28 weeks gestational age and < 7 days of age	NA	NA	5 to < 8 85.5 to < 136.8	≥ 8 ≥ 136.8
7 to 28 days of age (breast feeding)	5 to < 10 85.5 to < 171	10 to < 20 171 to < 342	20 to < 25 342 to < 427.5	≥ 25 ≥ 427.5
7 to 28 days of age (not breast feeding)	1.1 to < 1.6 x ULN	1.6 to < 2.6 x ULN	2.6 to < 5.0 x ULN	≥ 5.0 x ULN

¹⁸ Severity grading for total bilirubin in neonates is complex because of rapidly changing total bilirubin normal ranges in the first week of life followed by the benign phenomenon of breast milk jaundice after the first week of life. Severity grading in this appendix corresponds approximately to cut-offs for indications for phototherapy at grade 3 and for exchange transfusion at grade 4.

¹⁹ A laboratory value of 1 mg/dL is equivalent to 17.1 $\mu\text{mol/L}$.

²⁰ Definitions: Term is defined as ≥ 37 weeks gestational age; near-term, as ≥ 35 weeks gestational age; preterm, as < 35 weeks gestational age; and neonate, as 0 to 28 days of age.

Signature Page for VV-CLIN-004817 v5.0

Objectives: Primary: 
To describe the pharmacokinetic (PK) parameters of berotralstat administered orally to pediatric subjects with HAE aged 2 to < 12 years old and weighing ≥ 12 kg. Secondary: 
To assess the safety and tolerability of berotralstat administered orally to pediatric subjects with HAE aged 2 to < 12 years old and weighing ≥ 12 kg.To summarize the effectiveness of berotralstat in pediatric subjects with HAE aged 2 to < 12 years old and weighing ≥ 12 kg. Exploratory: 
To assess the palatability/acceptability of berotralstat oral granules in pediatric subjects with HAE aged 2 to < 12 years old and weighing ≥ 12 kg. Endpoints: Primary: 
PK: The primary endpoint is the characterization of the PK profile of berotralstat in subjects aged 2 to < 12 years. Secondary: 
Safety: The frequency and severity of adverse events (AEs) and serious adverse events (SAEs), laboratory analyses (clinical chemistry, hematology, coagulation), height, weight, vital signs, electrocardiograms (ECGs), and physical examination findings.	

- Effectiveness: the frequency of attacks, duration of symptoms, anatomical location of attack, on-demand treatment, number of days with angioedema symptoms, assessment of attack severity, discontinuations due to lack of efficacy, and number of hospitalizations and clinic visits from Week 1 through Weeks 12 and 48.

Exploratory:

- Age-appropriate questionnaire for palatability/acceptability of berotralstat oral granules as assessed by the site following the first dose.

Methodology:

This is a single-arm, open-label study designed to evaluate the PK of berotralstat; plasma concentrations of berotralstat will be measured and used in population PK analyses, allowing for determination of the appropriate weight-based dose for pediatric patients 2 to < 12 years old. In addition, the safety and tolerability of berotralstat will be assessed when given to pediatric subjects who are 2 to < 12 years old as a prophylactic treatment to prevent attacks of HAE. The effectiveness of berotralstat in this population will be summarized using descriptive statistical methods. Subjects will be enrolled into 4 or more dose cohorts; subject weight will be used to determine assignment to each cohort with the higher weight cohorts (Cohorts 1 and 2) enrolling first and in parallel. Cohort 3 will open for enrollment and initiate the 12-week standard-of-care (SOC) phase after ≥ 4 subjects from Cohorts 1 and 2, with ≥ 2 of the subjects from Cohort 2, have reached Week 2. Cohort 4 will open for enrollment and initiate the 12-week SOC phase after ≥ 4 subjects in Cohort 3 have reached Week 2. BioCryst will notify sites when Cohorts 3 and 4 are open for enrollment. Safety assessments by the Data Monitoring Committee (DMC) and PK modelling from all available PK data to confirm the weight band for the cohorts will occur prior to dosing subjects in Cohorts 3 and 4 with berotralstat. Additional dose cohort(s) may be added if indicated based on safety and/or population PK analyses with DMC endorsement.

This study will consist of 2 treatment periods: a 12-week SOC treatment period followed by an open-label berotralstat treatment period lasting up to 144 weeks. The berotralstat treatment period is divided into 3 parts as defined below. Throughout the study, site personnel will monitor subject safety through a combination of in-person clinic visits and tele-communication with the parent/caregiver(s) (P/C). The tele-contact may be either a telephone call or telemedicine visit conducted over the internet.

SOC Treatment Period: Subjects will continue taking their SOC therapy for HAE (either short-term or long-term prophylaxis, or acute treatment for HAE attacks) for 12 weeks from the screening visit. No additional in-person visits are required during the SOC treatment period; however, at approximately 4 and 8 weeks following screening, site personnel will contact the P/C to assess AEs and the overall status of the subject.

Part 1: After 12 weeks on SOC, subjects will return to the site for the Day 1 (baseline) visit. Prior to the Day 1 visit, subjects must discontinue all prophylaxis for prevention of HAE attacks; use of on-demand medication to manage acute HAE attacks may continue throughout the study. At the Day 1 visit, the site will confirm concomitant medications, review subject diary entries, and discuss any AEs that occurred during the SOC treatment period. If study activities were not completed satisfactorily during this time (eg, diary entries were incomplete or the P/C was not reachable to assess AEs at the prescribed intervals), the subject may be discontinued from the study prior to the berotralstat treatment period at the sole discretion of the investigator. Beginning on Day 1, subjects will take berotralstat orally once each day, with food, for 12 weeks. Additional study visits in Part 1 will occur at Weeks 2, 6, and 12. All safety assessments will be assessed at each visit. In addition to the clinic visits, the site will contact the P/C at Week 9 to assess safety and subject status.

Part 2: Beginning at the Week 12 visit, all subjects will be provided continued access to open-label berotralstat through Week 48 (a total of 36 weeks). Study visits in Part 2 will occur every 12 weeks

(Weeks 24, 36, and 48). Also, during Part 2, sites will contact the P/C at 4-week intervals between study visits (ie, at Weeks 16, 20, 28, 32, 40, and 44) to assess the subjects' overall wellbeing. The contact should be an arranged tele-contact; however, it may become an on-site visit if the investigator or P/C considers an in-person visit necessary for medical management of the subject. HAE attack details will only be collected through Parts 1 and 2.

Part 3: After Week 48, subjects may continue to receive open label berotralstat in Part 3 (Weeks 48 through 144; a total of 96 weeks). Visits in Part 3 will occur every 24 weeks: Weeks 72, 96, 120, and 144. Also, during Part 3, sites will contact the P/C at 12-week intervals between study visits (ie, at Weeks 60, 84, 108, and 132) to assess the subjects' overall wellbeing. The contact should be an arranged tele-contact; however, it may become an on-site visit if the investigator or P/C considers an in-person visit necessary for medical management of the subject. Berotralstat will be provided in Part 3 through Study Week 144 or until another mechanism is available to provide drug to the subject (eg, market access, separate study) or the sponsor discontinues development of the product for the prevention of angioedema attacks in children < 12 years of age.

Subjects who discontinue berotralstat at Week 144 or earlier will be required to attend an end of study (EOS) follow-up visit 3 weeks after study drug discontinuation. Subjects who discontinue the study but will continue to receive berotralstat via another mechanism will have EOS assessments performed at their last regularly scheduled visit.

PK Assessments: At Week 2 (in Part 1), plasma samples for PK analysis will be collected immediately prior to dosing and at designated timepoints post dose. Based on the PK results, the dose regimen of berotralstat may be adjusted for an individual subject or for all subjects in the cohort to ensure the exposure falls within the acceptable safety range; the dose of berotralstat will not be adjusted based on changes to the subject's weight during Part 1. In Part 2, one random sample for PK analysis will be drawn at Weeks 12, 24, 36, and 48. Reduced PK sampling may be performed in smaller subjects, especially subjects in Cohort 4, to maintain blood sample volumes within acceptable ranges. Additional PK samples may be drawn if the berotralstat dose is adjusted.

Number of subjects (planned):

Approximately 30 subjects are planned to be enrolled.

Main criteria for inclusion:

1. Age 2 to < 12 years of age and weighing \geq 12 kg.
2. Parent/caregiver willing and able to provide written, informed consent (with assent from the child where appropriate).
3. Subjects with a clinical diagnosis of HAE. A clinical diagnosis of HAE is defined as:
 - a. Screening results that documented immunogenic C1 esterase inhibitor (C1-INH) antigenic level below the lower limit of normal (LLN) reference range or C1-INH function < 50% and a complement 4 (C4) level below the LLN reference range.OR
 - b. Laboratory documentation of historical C1-INH functional level below the assay LLN.OR

- c. For subjects with C1-INH function $\geq 50\%$ but less than the assay LLN, a SERPING-1 gene mutation known or likely to be associated with HAE Type I or II, as assessed during the screening period OR a repeat C1-INH functional level $< 50\%$ will be considered acceptable for enrollment.
OR
 - d. Historical or new laboratory documentation of a SERPING-1 mutation known or likely to be associated with HAE.
OR
 - e. For subjects who currently use plasma-derived or recombinant C1-INH-based prophylactic therapies, a confirmed family history of C1-INH deficiency.
- 4. For subjects who are not currently receiving prophylaxis for HAE, documented history of ≥ 2 HAE attacks in the 6 months prior to the enrollment visit.
 - 5. Access to and ability to use 1 or more acute medications approved by the relevant competent authority for the treatment of acute attacks of HAE.
 - 6. In the opinion of the investigator, the subject would benefit from long-term oral prophylaxis.
 - 7. If sexually active, or become sexually active during the study, must agree to the use of effective contraception.

Main criteria for exclusion:

- 1. Concurrent diagnosis of any other type of recurrent angioedema.
- 2. Any clinically significant history of angina, myocardial infarction, syncope, clinically significant cardiac arrhythmias, left ventricular hypertrophy, cardiomyopathy, myocarditis, pericarditis, congenital heart defects, or any other clinically significant cardiovascular abnormality such as poorly controlled hypertension.
- 3. Known family history of sudden cardiac death at a young age (ie, < 40 years of age). Family history of sudden death from HAE is not exclusionary.
- 4. History of or current implanted defibrillator or pacemaker.
- 5. Moderate to severe hepatic impairment (Child-Pugh B or C).
- 6. A calculated creatinine clearance using the Modified Schwartz formula of ≤ 30 mL/min/1.73 m² or aspartate aminotransferase or alanine aminotransferase value $\geq 3 \times$ the upper limit of the age-appropriate normal reference range value.
- 7. History of severe hypersensitivity to multiple medicinal products or severe hypersensitivity/anaphylaxis with unclear etiology.
- 8. Current participation in any other investigational drug study or received another investigational drug within 30 days of enrollment; not willing to refrain from participation in another clinical study after

enrollment and for the duration of the study. [Note: drugs/vaccines approved under Food and Drug Administration (FDA) emergency use authorization (or country-specific analogous regulations) are not considered excluded or prohibited under this criterion.]

9. An immediate family relationship to either sponsor employees, the investigator, or employees of the study site named on the delegation log.
10. Any result at screening that, in the opinion of the investigator, is clinically significant and relevant for this study.
11. Any clinically significant medical condition or medical history (including altered mental status) that, in the opinion of the investigator or sponsor, would interfere with the subject's safety or ability to participate in the study. Examples include but are not limited to active malignancy under treatment, uncontrolled cardiovascular disease, organ dysfunction requiring supportive care.
12. Clinically significant abnormal ECG including but not limited to, a corrected QT interval calculated using Fridericia's correction ($QTcF = QT/RR^{0.33}$) > 450 msec, or ventricular and/or atrial premature contractions that are more frequent than occasional, and/or as couplets or higher in grouping.
13. Known hypersensitivity to berotralstat or any of its formulation excipients.

Investigational product, dosage, and mode of administration:

Berotralstat 150 mg capsules in multidose bottles and granules for oral administration packaged in unit-dose packets will be taken orally, once daily (QD), with food. The doses for Cohorts 1, 2, 3, and 4 are shown in the table below. Based on safety assessments and/or the PK data analyses, the weight bands for Cohorts 3 and 4 may be adjusted if needed.

The berotralstat dose for Part 1 will be determined based on subject weight on Day 1; this dose will be changed for an individual subject or for all subjects in the cohort if indicated by safety and/or PK parameters. In Parts 2 and 3, subjects will continue open label berotralstat for a total of up to an additional 132 weeks. The dose in Parts 2 and 3 will be based on subject weight and may be adjusted throughout the 132-week treatment period as indicated based on changes in the subject's weight, safety and/or PK parameters.

Cohort	Dose	Minimum Target Enrollment ^a	Weight Band (From PK modelling)
1	150 mg capsule	n=4	≥ 40 kg
2	108 mg granules	n=4	32 to < 40 kg
3	96 mg granules	n=4	24 to < 32 kg
4	78 mg granules	n=3	12 to < 24 kg

Note: Additional dose strengths ranging from 60 to <150 mg and/or cohorts may be utilized as indicated based on safety and/or PK results.

^a The n represents the minimum number that will be enrolled into each cohort. Since the total target enrollment is approximately 30 subjects, additional subjects will be enrolled into 1 or more of the cohorts or additional dose cohort(s) may be added. Subject enrollment in any 1 or more cohorts may be suspended to ensure sufficient enrollment of subjects in each cohort.

Reference therapy, dosage, and mode of administration:

This is an open-label trial, and there is no reference therapy. Subjects will remain on their SOC regimen for the 12-weeks comprising the SOC treatment period. SOC may include short-term prophylaxis, long-term prophylaxis, and/or on-demand treatment for acute attacks. Data on AEs and HAE attacks will be collected during this period.

Duration of treatment:

Subjects will continue to take their SOC for 12 weeks following screening. Subjects who continue in the study will take berotralstat capsules (150 mg) or granules for oral administration (in unit-dose packets) for 12 weeks (Part 1) beginning on Day 1. For Parts 2 and 3, subjects will take berotralstat through Weeks 48 (Part 2) and 144 (Part 3), respectively.

Criteria for evaluation:

Pharmacokinetics:

Plasma PK concentrations will be analyzed using population PK methodology and reported in a separate stand-alone pharmacometric report.

Safety:

Frequency and severity of AEs/SAEs, laboratory analyses (clinical chemistry, hematology, coagulation), height, weight, vital signs, ECGs, and physical examinations.

Effectiveness:

Number of angioedema attacks (timing, duration of symptoms, anatomical location, treatment), number of days with angioedema symptoms, assessment of attack severity, discontinuations due to lack of efficacy, and number of hospitalizations and clinic visits through Week 48.

Statistical methods: Descriptive statistics will be generated for PK, safety, and effectiveness endpoints. Summaries will include sample size (n), mean, standard deviation (SD) and/or standard error of the mean (SEM), median, minimum, and maximum for continuous variables, and counts/frequencies and percent for categorical variables. Results will be presented by weight cohort and study visit where applicable. Interim analyses may be conducted after at least 15 subjects complete 48 weeks of treatment (Part 2) and/or after all subjects complete 48 weeks of treatment. Additional interim analyses may be done during the course of the study as needed to support regulatory filings, safety updates, and publications. No inferential analyses are planned. The final analysis will be conducted following the last study visit and after database lock has occurred.

Pharmacokinetics:

Standard noncompartmental methods will be used to calculate the following individual subject PK parameters from observed plasma concentrations: maximum plasma concentration (C_{max}), area under the concentration-time curve from time 0 to the last measurable concentration (AUC_{0-last}), area under the concentration-time curve from time 0 to 6 hours post-dose (AUC_{0-6}), time to C_{max} (T_{max}), last measurable concentration (C_{last}), and time to C_{last} (T_{last}) as data permit. Descriptive statistics will be calculated for each parameter and may be stratified by cohort and dosing regimen as appropriate.

Population PK modeling approach will be used to estimate the following PK parameters: AUC over the dosing interval (AUC_{tau}) at steady state, C_{max} at steady state, T_{max} , average plasma concentration (C_{avg}) at steady state, concentration at the end of a dosing interval (C_{trough}) at steady state, apparent clearance (CL/F), and apparent total volume of distribution (V_{ss}/F). The results of these analyses will be reported in the stand-alone pharmacometric report.

Safety:

